3.4 Known Potential Benefits

Vaccine against *V. cholerae* is intended to protect the immunized in endemic areas, as well as travelers (including military personnel) from industrialized countries to regions endemic for *V. cholerae*, and in the event of a threat or exposure to a biological weapon. There is no known benefit to receipt of off-label use of the CVD 103-HgR vaccine.

V. cholerae is a global pathogen that can disseminate rapidly in settings where there is crowding and inadequate sanitation. The symptoms of cholera are predominantly a rapidly dehydrating diarrheal disease without significant systemic toxicity.

This clinical research study is intended to greatly further our understanding of the protective immunological mechanisms that can be elicited systemically. This information is intended to inform the development of newer generation cholera vaccines.

3.5 Risk/Benefit Ratio

Alternative approaches are limited for these studies. The risks of the study interventions are low. The CVD 103-HgR vaccine has been extensively used, and their side effect profiles are tolerable and well-understood. Venipuncture also carries a low risk when conducted by a trained phlebotomist. On the other hand, enteric infections are widespread throughout the globe and are associated with significant morbidity and mortality. The complexity of the immune response after vaccination cannot be reproduced in other environments. The risks associated with the procedures described in this protocol are small compared to the potential general benefit of better understanding the protective immunity elicited by these vaccines.

3.6 Specimen Management

All specimens collected through this protocol will be labelled with the volunteer identification number and date, but not any volunteer identifiable information (such as date of birth). Specimens that are processed for storage will also be labelled in a manner which is de-identified and contains no identifiable information. Specimens are entered into specimen tracking form to link them with the volunteer identification number. Only the clinical PIs and study coordinator(s) will have access to the linking information. Specimen handling, processing, and storage will be according to internal CVD standard operating procedures.

4 STUDY ENROLLMENT AND WITHDRAWAL

The study enrollment will include adults from the local area. The study will not exclude any race, ethnicity or gender from enrollment. Women of child bearing potential will have a urine pregnancy test prior to vaccination. Women testing positive will be excluded from the study. Volunteers will have frequent contact with the study coordinator(s) to facilitate retention and complete data collection. The inclusion/exclusion criteria will be reviewed with each volunteer during the consent process. The clinical principal investigator or designee is responsible for reviewing and signing off the inclusion and exclusion criteria for all enrollees.

4.1 Informed Consent

All aspects of the protocol will be explained in depth to volunteers including the specific purpose of the blood draws. Volunteers will be given a schedule of when, where, and how much blood will be drawn. The consent form will be read by the volunteer and ample time for questions and answers will be provided. Interested volunteers will provide written consent prior to any procedures being performed. Volunteers will remain enrolled as a blood donor as long as the laboratory has need for the blood (which may continue for several years), or until the volunteer withdraws consent. The informed consent process and other health assessment questions will take place in a private or semi-private room. Privacy and confidentiality of the volunteer will be maintained.

4.2 Inclusion Criteria

Volunteers must meet all inclusion criteria in order to be eligible to participate.

1. Age 18 years to 64 years at the time of enrollment
2. Good general health as determined by a screening evaluation within 28 days before blood donation or vaccination
3. Provides written informed consent prior to initiation of any study procedures

4.3 Exclusion Criteria

Volunteers must meet no exclusion criteria in order to be eligible to participate

1. History of any of the following medical conditions:
 - Diabetes
 - Cancer in past 5 years (except for basal cell carcinoma of the skin and cervical carcinoma in situ)
 - Heart disease (e.g., hospitalization for a heart attack, coronary artery bypass graft, arrhythmia, or syncope, within past 5 years. Current symptoms of heart disease, such as dyspnea, angina, or orthopnea)
 - Recurrent infections (e.g., more than 3 hospitalizations for invasive bacterial

- infections such as pneumonia or meningitis)
- Current drug or alcohol abuse
- Active ulcer disease or ongoing intestinal condition
- Treatment for anemia in last 6 months
- Treatment with anti-malarial drugs within ten days prior to study vaccination
- Treatment with antibiotics within 14 days prior to study vaccination
- Immunodeficiency or immunosuppression from illness or treatment

2. Close contact within 7 days following study vaccination with a person who has an immunodeficiency or immunosuppression from illness or treatment
3. History of cholera infection or cholera vaccination
4. Any of the following CBC abnormalities during screening:
 - WBC $<0.81 \times \text{LLN}$ or $>1.09 \times \text{ULN}$
 - Hemoglobin $<0.91 \times \text{LLN}$ or $>1.18 \times \text{ULN}$ (women) or $<0.92 \times \text{LLN}$ or $>1.18 \times \text{ULN}$ (men)
 - Platelet count $<0.8 \times \text{LLN}$ or $>1.2 \times \text{ULN}$
5. Any of the following laboratory abnormalities during screening:
 - SGOT or SGPT >1.5 times normal
 - Positive serology for HIV antibody
6. Poor peripheral venous access for blood donation
7. Other condition that the opinion of the investigator would jeopardize the safety or rights of a volunteer participating in the trial or interfere with the scientific integrity of study
8. Positive urine pregnancy test (HCG) on the day of vaccination

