2.2 Outcome Measures

2.2.1 Primary outcome

Percentage of responders by four-fold increase in vibriocidal antibody titers between pre- and post-immunization time-points.

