4.4 Delayed Vaccination

Study participants that have an acute illness, fever, or gastrointestinal complaint (temporary) within the 3 days prior to scheduled vaccination should have their vaccination delayed until recovery from their temporary illness. Study participants that are on a temporary course of concomitant antibiotics should have their vaccination delayed until at least 7 days after completion of antibiotics. Study participants on certain potentially interfering malaria prophylaxis medications (chloroquine), should have their vaccination delayed—dosing may begin 2 weeks after completion of chloroquine.

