7.2 Sample Size Considerations

This study is exploratory in nature and is designed to identify associations among the presence and quantity of various intestinal bacteria, immune responses and clinical outcome. Thus it is designed to generate hypotheses but not to test any specific hypothesis based on prior data since no such data is available in the literature. The sample sizes planned for the study are therefore based on feasibility rather than power to reject any specific hypothesis. For large differences between groups the study will have good power to find statistically significant associations.

Data for withdrawn volunteers will be included in the intent to treat group. We anticipate a dropout rate of 20%. This is consistent with other studies of this nature performed at the University of Maryland.

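### The delay after antibiotics in section 4.4 (7 days) is shorter than the exclusion in section 4.3 (14 days), so a dose on days 7 to 13 can follow one rule and breach the other

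*Combined protocol and SAP*

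**What the plan says.** Section 4.3 opens with a mandatory rule: "Volunteers must meet no exclusion criteria in order to be eligible to participate". One listed exclusion is "Treatment with antibiotics within 14 days prior to study vaccination". The same list contains a criterion that can only be assessed at dosing: "Positive urine pregnancy test (HCG) on the day of vaccination".

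Section 4.4 deals with participants whose vaccination has to wait. Someone on a temporary antibiotic course "should have their vaccination delayed until at least 7 days after completion of antibiotics". For chloroquine, "dosing may begin 2 weeks after completion of chloroquine".

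Appendices A and B mark the inclusion/exclusion review at Visit 1 only, 7 to 28 days before vaccination. They also mark an interim history at Visit 2, the vaccination visit, but nothing says that it checks the antibiotic interval. Section 4.2 requires a "screening evaluation within 28 days before blood donation or vaccination".

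The primary outcome (section 2.2.1) is "Percentage of responders by four-fold increase in vibriocidal antibody titers" from before to after immunization. On analysis sets, section 7.2 says only this: "Data for withdrawn volunteers will be included in the intent to treat group".

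**The concern.** Two sections give different antibiotic-free intervals for the same dosing day, and neither is made subject to the other. Section 4.4 is the instruction written for a volunteer on antibiotics, so clinic staff would naturally turn to it, and it gives the shorter interval. This matters most for a course started after Visit 1, because the scheduled eligibility review is then already past.

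A volunteer dosed in the gap would meet an exclusion that the protocol itself set for a live oral vaccine, and would still enter the primary responder percentage. No passage removes such a volunteer, and section 7.2 keeps even withdrawn volunteers in the intent-to-treat group. What is at stake is a clear answer to whether a given volunteer may be dosed today, and who validly belongs in the primary result.

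**Working it through.** The plan has no figure of its own to reproduce here. The check compares the two day rules.

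**Inputs**
- Section 4.3: 14-day antibiotic window before vaccination, mandatory.
- Section 4.4: minimum delay of 7 days after the course ends.
- Section 4.2: screening no more than 28 days before vaccination.

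**Step 1: where the rules differ.** Let d be the days from the last antibiotic dose to vaccination, taking the end of the course as the last dose. Section 4.4 is met when d ≥ 7. Section 4.3 excludes when d < 14, or d ≤ 14 if the window includes day 14.

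| Days since last dose | Section 4.4 | Section 4.3 |
|---|---|---|
| 0 to 6 | delay | excluded |
| 7 to 13 | delay satisfied | excluded |
| 14 | delay satisfied | depends on how the window is read |
| 15 or more | delay satisfied | not excluded |

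The conflict covers 14 − 7 = 7 days, or 8 with day 14 included.

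**Step 2: an example.** A volunteer is screened 28 days before dosing, then takes a course that ends 10 days before dosing. Since 10 ≥ 7, section 4.4 is met. Since 10 < 14, section 4.3 excludes the volunteer.

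**Step 3: do both rules cover the same day?** Yes. The 4.3 window is counted back from vaccination, not from screening or enrollment, and the pregnancy criterion in the same list is tested on the vaccination day. Section 4.3 cannot be confined to screening.

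**Step 4: comparison with anti-malarials.** Section 4.3 sets ten days and section 4.4 sets 2 weeks for chloroquine. Since 14 > 10, following 4.4 also satisfies 4.3. For antibiotics the order is reversed (7 < 14), so following 4.4 does not satisfy 4.3.

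**Step 5: effect of moving to 14 days.** The move is m = 14 − d, from 14 − 13 = 1 day to 14 − 7 = 7 days. With s the days from screening to the original dosing date, re-screening is needed when s + m > 28.
- m = 7: 21 + 7 = 28 fits and 22 + 7 = 29 does not, so re-screening is needed for s = 22 to 28.
- m = 1: 27 + 1 = 28 fits and 28 + 1 = 29 does not, so re-screening is needed only for s = 28.

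With 14 days in both sections, counted from the last dose, the conflict falls from 7 (or 8) days to 0.

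**The case against.** The best defence is that both rules can be obeyed at once. Section 4.3 is mandatory, while 4.4 is worded as advice and sets only a floor, and meeting a floor does not waive an exclusion. The chloroquine sentence supports this cumulative reading: apply both sections and the longer interval always governs. On that view only a cross-reference is missing. This stands in part, since 14 days is the more likely intent. But a floor set too low is still a stated rule that lets an excluded volunteer be dosed, and the reader has to infer the precedence.

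Other safeguards exist. The investigator signs off the criteria for all enrollees (section 4). Section 4.3 has a general exclusion for conditions that would interfere with the study's scientific integrity. Section 4.5 allows removal when an exclusion criterion develops or a treatment might interfere with immune responses. Section 8.6 reviews eligibility and concomitant medication. None of these states an interval. The 4.5 provision is discretionary, and quality review comes after the dose.

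It may also seem harsh to call a dose that followed 4.4 a deviation. Section 8.5, however, defines a deviation as any noncompliance with the protocol, and a dose on days 7 to 13 does not comply with 4.3.

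The 56-day limit on repeat screening tests in section 3.2 might appear to block re-screening after a delay. It concerns planned repeats before scheduled donations, not renewal of a lapsed screening evaluation before vaccination.

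The objection that the consequence is small is accepted.

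**Conclusion.** The inconsistency is real. On days 7 to 13 after the last antibiotic dose (7 days, or 8 if day 14 counts as within the window), vaccination can follow section 4.4 and breach section 4.3, and no text settles which applies. The day count assumes that both rules are counted from the last dose.

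The point is minor. The documents give no number of volunteers likely to fall in the gap and no evidence that antibiotics finished 7 to 13 days earlier reduce the vibriocidal response, so no size of bias can be stated. The study is exploratory, sized on feasibility and has no success threshold, so no decision changes. What needs correcting is the eligibility rule and, through it, who validly counts in the primary responder percentage.

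**What to change.** - In section 4.4, raise the minimum delay after antibiotics from 7 to 14 days.
- In section 4.3, reword the exclusion as *last antibiotic dose less than 14 days before study vaccination*. Both sections then count from the same event and agree that day 14 is acceptable.
- State that the Visit 2 interim history confirms this interval before dosing.
- If any volunteer has already been dosed 7 to 13 days after antibiotics, record it as a deviation under section 8.5.

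The cost is two amended sentences and one existing visit step made explicit. Affected vaccinations move by 1 to 7 days, with repeat screening only where the move passes the 28-day limit in section 4.2.

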4.4 Delayed Vaccination

Study participants that have an acute illness, fever, or gastrointestinal complaint (temporary) within the 3 days prior to scheduled vaccination should have their vaccination delayed until recovery from their temporary illness. Study participants that are on a temporary course of concomitant antibiotics should have their vaccination delayed until at least 7 days after completion of antibiotics. Study participants on certain potentially interfering malaria prophylaxis medications (chloroquine), should have their vaccination delayed—dosing may begin 2 weeks after completion of chloroquine.

4.5 Withdrawal

A study volunteer will be discontinued from study participation for the following reasons:

- Request by volunteer to terminate participation
- Requirement for prohibited concomitant medication or treatment
- Unable to comply with requirements of the protocol
- Failure to comply with study procedures
- At the request of the IRB or NIAID
- The volunteer's well-being, based on the opinion of the investigator

The PI may remove volunteers from the study if they develop adverse events (AEs) that are believed to be related to the study or unrelated but may impact the safety of the volunteer or the integrity of the study. These might include abnormal laboratory values or test procedure results, medical treatments that might interfere with immune responses or use of other investigational products or vaccines during the study period. Development of exclusion criteria may also prompt exclusion from the study. Volunteers may also be withdrawn for failure to comply with study procedures. Volunteers may withdraw consent at any time upon request.

4.6 Termination of the Study

This study may be closed by the NIH, the principal investigator, or the UMB IRB. If the study is terminated prematurely the study participants will be notified in writing. A final safety evaluation will be done for all volunteers enrolled at the termination of the study.

5 INVESTIGATIONAL PRODUCT(S)

5.1 Cholera Vaccine (CVD 103-HgR)

5.1.1 Formulation, Packaging, and Labeling

CVD 103-HgR, marketed as Vaxchora®, is provided as two powder sachets, containing buffer and lyophilized organisms, in a single package.

5.1.2 Acquisition

Product will be obtained from the manufacturer PaxVax, Inc (Redwood City, CA, U.S.A.)

5.1.3 Product Storage, Stability, and Expiration

Vaxchora (Cholera Vaccine, Live, Oral) is to be stored at -15° C or colder (5° F or colder). Each package of vaccine shows an expiration date. This expiration date is valid only if the product has been maintained at -15° C or colder.

5.1.4 Preparation/Handling/Administration

Vaxchora (Cholera Vaccine, Live, Oral; CVD 103-HgR) is indicated for immunization of adults 18-64 years of age against disease caused by *V. cholerae*. [NOTE: *Vaxchora* is currently not licensed for older adults (age 65 years or older) and thus older adults are not intended to be vaccinated with Vaxchora in this study.] Vaccine potency is dependent upon storage under freezing (-15° C or colder; 5° F or colder). The vaccine should be reconstituted and ingested within 15 minutes of removing from the freezer. Recipients should avoid eating or drinking for 60 minutes before and after ingestion of Vaxchora.

Participant will take a single oral dose of the CVD 103-HgR vaccine. A volume of ~100 mL of purified bottled water (at cold or room temperature) shall be placed into a clean disposable cup. The buffer component sachet is emptied into the cup and stirred. Then, the active vaccine (lyophilized *V. cholerae* CVD 103-HgR) component is emptied into the cup and stirred, for ~30 seconds. The mixed contents should be completely consumed within 15 minutes of removal from the freezer.

5.2 Maintaining Blind for Investigational Product(s)

This study is not blinded.

5.3 Accountability/Final Disposition for the Investigational Product(s)

Vaccine will be kept in a secure area and stored according to package directions. The CVD will maintain an accurate record of shipping and dispensing of investigational products in an accountability ledger. The ledger will include the date and amount of investigational product dispensed to each volunteer.

6 MANAGEMENT OF SAFETY

6.1 Specification of Safety Parameters

The clinical investigators are responsible for reporting Adverse Events (AEs) that are observed or reported during the study. Serious Adverse Events (SAEs) must be reported as soon as the clinical-investigators become aware. See Section 7.2 for reporting windows. Only AEs and SAEs occurring within 7 days post vaccination determined to be related to the study product or 1 day post blood donation will be collected. No AE or SAE will be collected outside the window mentioned above.

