6.2 Methods and Timing for Assessing, Recording, and Analyzing Safety Parameters

Adverse Event (AE)

ICH E6 defines an AE as any untoward medical occurrence in a patient or clinical investigation volunteer administered a pharmaceutical product regardless of its causal relationship to the study treatment. An AE can therefore be any unfavorable and unintended sign (including an abnormal laboratory finding), symptom, or disease temporally associated with the use of medicinal (investigational) product. The occurrence of an AE may come to the attention of study personnel during study visits and interviews of a study recipient presenting for medical care, or upon review by a study monitor.

All AEs including local and systemic reactions not meeting the criteria for “serious adverse events” should be captured on the appropriate CRF. Information to be collected includes event description, time of onset, clinician’s assessment of severity, relationship to study product (assessed only by those with the training and authority to make a diagnosis, which would include MD, PA, Nurse Practitioner, DO, or DDS), and time of resolution/stabilization of the event. All AEs occurring while on study must be documented appropriately, AEs occurring within 7 days post vaccination determined to be related to the study product and/or 1 day post-blood donation and determined to be related to the procedure will be collected. All AEs will be followed to adequate resolution.

Any medical condition that is present at the time that the patient is screened should be considered as baseline and not reported as an AE. However, if it deteriorates at any time during the study, it should be recorded as an AE.

All AEs must be graded for severity and relationship to study product. FDA defines an AE as any untoward medical occurrence associated with the use of a drug in humans, whether or not considered drug related.

Severity of Event: The following guidelines will be used to quantify intensity.

Mild: events require minimal or no treatment and do not interfere with the patient’s daily activities.

Moderate: events result in a low level of inconvenience or concern with the therapeutic measures. Moderate events may cause some interference with functioning.

Severe: events interrupt a patient’s usual daily activity and may require systemic drug therapy

or other treatment. Severe events are usually incapacitating.

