Life threatening: any adverse drug experience that places the patient or volunteer, in the view of the investigator, at immediate risk of death from the reaction as it occurred, ie, it does not include a reaction that had it occurred in a more severe form, might have caused death.

Changes in the severity of an AE should be documented to allow an assessment of the duration of the event at each level of intensity to be performed. Adverse events characterized as intermittent require documentation of onset and duration of each episode.

Relationship to Study Products: The clinician's assessment of an AE's relationship to vaccine is part of the documentation process, but it is not a factor in determining what is or is not reported in the study. If there is any doubt as to whether a clinical observation is an AE, the event should be reported. All AEs must have their relationship to study product assessed using the terms: related or not related. In a clinical study, the study product must always be suspect. To help assess, the following guidelines are used.

- **Related** – There is a reasonable possibility that the study product caused the adverse event. Reasonable possibility means that there is evidence to suggest a causal relationship between the study product and the adverse event.
- **Not Related** – There is **not** a reasonable possibility that the administration of the study product caused the event.

Serious Adverse Event (SAE)

An adverse event or suspected adverse reaction is considered "serious" if, in the view of either the investigator or sponsor, it results in any of the following outcomes:

- death,
- a life-threatening adverse event*,
- inpatient hospitalization or prolongation of existing hospitalization,
- a persistent or significant incapacity or substantial disruption of the ability to conduct normal life functions, or
- a congenital anomaly/birth defect.
- important medical events that may not result in death, be life-threatening, or require hospitalizations may be considered serious when, based upon appropriate medical judgment they may jeopardize the patient or volunteer and may require medical or surgical intervention to prevent one of the outcomes listed in this definition. Examples of such medical events include allergic bronchospasm requiring intensive treatment in an emergency room or at home, blood dyscrasias or convulsions that do not result in inpatient hospitalization, or the development of drug dependency or drug abuse.

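### Sections 6.1 and 6.2 give conflicting rules on which adverse events are collected, both by relatedness and by time window

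*Combined protocol and SAP*

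**What the plan says.** The restricting text appears in two places. Section 6.1 collects "Only AEs and SAEs occurring within 7 days post vaccination determined to be related to the study product", adds a window of one day after blood donation, and closes with "No AE or SAE will be collected outside the window mentioned above". Section 6.2 repeats the vaccine-window limit for AEs ("AEs occurring within 7 days post vaccination determined to be related to the study product and/or") and, for the day after a donation, requires the event to be related to the procedure.

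The wider text is all in 6.2:

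- AEs that are not serious "should be captured on the appropriate CRF". That sentence sets no window and no causality condition.
- "All AEs occurring while on study must be documented appropriately".
- A condition present at screening that worsens at any point on study is to be recorded as an AE.
- Under the Relationship to Study Products paragraph, the clinician's causality assessment is part of the documentation, but "it is not a factor in determining what is or is not reported in the study". The same paragraph adds: "All AEs must have their relationship to study product assessed using the terms: related or not related".
- Under the Serious Adverse Event heading, all SAEs go on the SAE CRF and are followed and reviewed by a study clinician.

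Section 6.3 has the Independent Safety Monitor (ISM) receive, review and manage AEs and SAEs. Section 6.1 refers the reader to Section 7.2 for reporting windows.

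**The concern.** Site staff have two sets of instructions and cannot obey both. Which events enter the record then depends on which sentence a staff member follows, and any AE listing would be hard to interpret.

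The relatedness filter matters most. A causality call made at the site becomes the condition for an event being collected at all, so a wrong call of unrelated leaves no collected entry that someone else could revisit. Section 4.5 also lets the PI remove a volunteer for an unrelated AE that bears on safety. Under the filter, such an event falling only in the vaccine window would be missing from the collected AE record.

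The bar outside the windows raises a separate problem. Section 3.3 names anemia as a study risk, and 6.2 counts an abnormal laboratory finding as a possible AE. A low hemoglobin found at a repeat screen, well after the last draw, could be an AE under 6.2 that 6.1 says not to collect.

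**Working it through.** The plan gives no figure to reproduce, so the check is a comparison of text. It uses four example events, chosen to separate the rules; they are not a count of anything.

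| Example event | 6.1 | 6.2, collection sentence | 6.2, other text |
|---|---|---|---|
| A. Non-serious, unrelated, 5 days after vaccination, no draw in the preceding day | Not collected | Not collected | On the CRF; relatedness not to decide |
| B. SAE in year 3, weeks after the last draw | Not collected | Not covered | On the SAE CRF |
| C. Baseline condition worsens at month 6, outside both windows | Not collected | Not covered | Recorded as an AE |
| D. Non-serious, the day after a draw, unrelated to the procedure, beyond 7 days from vaccination | Unclear | Not collected | On the CRF |

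**Relatedness (A).** The requirement to class every AE as related or not related could, alone, coexist with a filter: assess everything, collect only the related. It cannot coexist with the statement that relatedness does not govern what is reported, unless reporting and collecting are different acts. Under the filter, the not-related class would be empty among collected events that fall only in the vaccine window.

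**Timing (B, C).** The bar in 6.1 covers both AEs and SAEs. The SAE list in 6.2 has no window, and the rule on baseline conditions has none by its terms.

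**Where the conflict sits.** In 6.2 the duty to document all on-study AEs and the restricted collection rule are two halves of one sentence. Editing 6.1 alone would leave that contradiction in place.

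**Donation window (D).** Section 6.2 states the procedure-relatedness condition outright. In 6.1 the sentence is elliptical: the relatedness phrase may apply to the vaccine window only or carry over to donations.

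**Pointer.** Section 7.2 is Sample Size Considerations. The 5-working-day SAE reporting rule is in 6.2.

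**Time over which the rules diverge (illustration only).** Inputs: follow-up of up to 8 years (Section 3) and 1 to 20 draws a year for serial donors (3.2). Taking 8 years as 8 × 365.25 = 2,922 days and ignoring overlap:

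- at 1 draw a year, windows cover (7 + 8 × 1) / 2,922 = 15 / 2,922 = 0.5%;
- at 20 draws a year, (7 + 8 × 20) / 2,922 = 167 / 2,922 = 5.7%.

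So about 94% to 99.5% of a full 8-year follow-up lies outside the 6.1 windows. This is a share of days, not of events.

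**The case against.** The best defence is that restricted collection is deliberate. This is an open-label specimen-collection study of a licensed vaccine, with no safety objective or outcome, and 6.2 states that reactogenicity is not measured. The windowed rule appears twice, so the broader sentences may be general AE text left unadjusted. That may well be the intention, and limited collection can be a legitimate choice. But the protocol does not say the specific rule overrides the general ones, and the general ones name the CRF.

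A second defence separates the verbs. *Documented* or *reported* may mean something other than *collected*, and 6.1 itself opens by making investigators responsible for reporting AEs and for prompt reporting of SAEs. The protocol defines no such distinction, and it would not remove the clash over CRF entries. It does limit the claim about oversight. A reader might infer that the ISM cannot see unrelated events. The documents do not establish that, because 6.3 does not say whether the ISM receives only collected events.

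Other stronger readings also fail:

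- It is tempting to set "If there is any doubt as to whether a clinical observation is an AE, the event should be reported" against the filter, but that sentence concerns whether something is an AE, not what caused it.
- Section 6.6 might look like another contradiction. It covers IRB reporting of suspected-related SAEs learned of after study completion, not what is collected during the study.
- Section 6.1 should not be read as plainly free of a relatedness condition for donations; it is unclear.
- Counting event types under each rule would not measure the harm. It would mix relatedness to the product with relatedness to the procedure and count rules, not events.

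Overlap also narrows the loss on one reading. If 6.1's donation window is unfiltered, the typical Appendix B draws on Days 1, 3 and 8 leave roughly Days 5 to 7 as vaccine window only. That schedule is not binding, and 6.2's procedure condition would restore the filter. Interim history at visits and the clinical PIs' review (6.9) mean the site may still learn of such events, though that review is not independent.

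**Conclusion.** The contradiction is real, and no other section resolves it. It has two parts: the relatedness filter (6.1 and the collection sentence in 6.2) against the causality and CRF text in 6.2, and the out-of-window bar in 6.1 against the CRF, SAE and baseline-deterioration rules in 6.2. The unclear donation condition in 6.1 and the wrong pointer are minor additions.

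The consequence is confined to the completeness of the safety record and its review. The effect on the ISM is conditional on its receiving only collected events. The primary outcome (four-fold rise in vibriocidal titer) and the immunological analyses do not use these data. How many events would be lost cannot be derived from the documents, which also do not show which rule was intended. This should be fixed as an inconsistency; it is not evidence that restricted collection is in itself improper.

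**What to change.** 1. Put one identical collection rule in 6.1 and 6.2. The version consistent with the Relationship to Study Products paragraph is to collect every AE and SAE in the existing 7-day post-vaccination and 1-day post-donation windows, whatever the cause, and then record the related or not-related assessment. If restricted collection is intended, rewrite the general AE, causality and SAE text of 6.2 so that it says so.
2. Reconcile the out-of-window bar with 6.2, stating which SAEs and which baseline deteriorations outside the windows are recorded, and where.
3. Use the same donation-window condition in both sections.
4. Replace the pointer to Section 7.2 with one to the section holding the reporting rules.

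Items 3 and 4 are wording only. Item 1, in the version that collects regardless of cause, adds entries on existing CRFs within the existing windows, with no new visits or tests; their number cannot be estimated. The burden from item 2 depends on what the sponsor decides. Collecting all AEs over the full follow-up would be a much larger undertaking, and it is not what is proposed here.
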